7.6.6. Laboratory, Vital Signs and Physical Examination

A listing of all laboratory values will be made, restricted to participants with at least one laboratory abnormality.

Physical examination findings will be summarized at baseline. A listing of the abnormalities will be made.

Vital signs including temperature, pulse/heart rate, respiratory rate, and blood pressure (systolic and diastolic) will be summarized over time, using descriptive statistics. Abnormalities emerging after vaccination will be tabulated by worst abnormality grade using the FDA table in Appendix 3.

An abnormality (toxicity grade or abnormality based on normal ranges) will be considered as emerging in a particular period if it is worse than the baseline value. If the baseline is missing, the abnormality is always considered emerging. A shift from ‘abnormally low’ at baseline to ‘abnormally high’ post baseline (or vice versa) is also emerging. In case a laboratory test result is censored (no numeric value is available, but only a verbatim term) then a numeric value will be imputed by a value exceeding the cut-off value with one unit. (<x: subtract 1 unit from x, >x: add 1 unit to x; <3.45 is imputed with 3.44).

In case no toxicity grades are defined for a test, the abnormalities (above/below normal range) will be used. In determining toxicity grades, the following rules are applied:

- Worst grades/abnormalities are determined over the whole observational period for each trial period separately, including all post-baseline measurements of that period.
- The abnormalities ‘abnormally low’ and ‘abnormally high’ are considered equally important, i.e. if a participant has as well an abnormally low as an abnormally high value post-baseline, both abnormalities are shown in the tables. (This means that the sum of the percentages can be more than 100%)
- Note: as the grading scale for some parameters in the grading table has some gaps (zones where no toxicity grade definition exists), laboratory results falling in these zones will be allocated to the adjacent worst-case grade.
- If a lab value falls within the grading as specified in the grading table but also within the local lab normal limits, the value is considered as normal.

For the grades, no distinction will be made between test results of samples obtained under fasting and under non-fasting conditions: in case limits under fasting and non-fasting conditions differ, the limits of the conditions (fasting/non-fasting) of scheduled visits as planned in the CTP will always be used, also for samples obtained under a different condition (e.g. samples of withdrawal visits).

A listing of participants with fever according to the FDA grading table will also be provided. In addition, temperature measurements (whether obtained from the diary or from on-site assessments) will be allocated to predefined temperature intervals (from 37.5° C until 40°C, in steps of half degree increments; eg <37.5, 37.5-<38, 38-<38.5, ... >40), and tabulated.

7.6.7. Safety Analyses After Receipt of the Ad hoc Booster Vaccination

Study participants who receive the ad hoc booster vaccination, will be removed from the main safety analyses as of that point in time^a. A separate safety analysis will be conducted on the study

^a Note that participants may already have been removed from the main safety analyses due to unblinding and/or receipt of an unscheduled vaccine (either a COVID-19 vaccine received outside of the study or after crossing over from

participants who received the ad hoc booster vaccination, starting at the time of the ad hoc booster vaccination and showing their post ad hoc booster vaccination 7 day reactogenicity data, their post ad hoc booster vaccination 28-day unsolicited AE data, and their post ad hoc booster vaccination SAE/AESI data, as available. The statistical analysis will be descriptive. It will show study participants according to their original vaccination regimen in tables, listings and figures. In addition, the analyses may also be conducted separately by subgroups of study participants who received a COVID-19 vaccine outside of the study vs study participants who did not receive a COVID-19 vaccine outside of the study. A distinction between mRNA vaccines vs other vaccines may be made, if the numbers are sufficiently high. Otherwise, this information will be included in the listings only.

7.7. Other Analyses

7.7.1. Immunogenicity Analyses

The analysis of immunogenicity will use the PPI set. Immunogenicity analyses will also be done on the FAS (participants who became infected during the study will be analyzed as a subgroup and shown in the graphs using different colors and symbols). Data will be analyzed by vaccine regimen, and by vaccine regimen and participant seropositivity status at screening^a. Data will be presented by scheduled time point. For the PPI analysis, samples taken outside of the allowed window will be excluded from the tables and graphs (but will be included in the listings and clearly marked as results not included in the PPI analyses). For the FAS analysis, samples taken outside of the allowed window will be included.

Note: analyses that are potentially unblinding at the individual participant level (e.g. graphs showing individual data tied to COVID-19 infection status, especially when the number of COVID-19 infections is low and/or when time of infection is indicated) will be carried out after official unblinding of the trial, or will be carried out exclusively on specific cohorts (or other clearly defined subgroups) after these are unblinded. Alternatively, prior to unblinding, these analyses can be performed in a completely blinded manner (e.g. tables with only a single column pooling all regimens).

7.7.1.1. Parameters

The following humoral and cellular immune responses may be measured. However, not all assays might be available for all immunogenicity analyses covered by this SAP. Further information on

placebo to active within the study). Refer to the clinical trial protocol amendment 15, section 9.7 for more information.

^a As indicated previously, all analyses, including the immunogenicity analyses, will be conducted by actually received vaccine (“as treated” principle). Note that the statistical tables are designed with the planned vaccine regimens as columns. Therefore, participants who receive e.g. “Placebo, Placebo” instead of “Ad26.COV2.S 5x10¹⁰ vp, Placebo” will appear in the “Placebo, Placebo” column. However, to avoid sparse columns, participants who receive e.g. “Placebo, Ad26.COV2.S 5x10¹⁰ vp” (which is not a planned vaccine regimen) will be excluded from the statistical tables. They will be included in the listings, as well as in the programmed patient narratives where they will appear as “Subjects with vaccine misallocation”.

which assays will be analyzed in each of the analyses, will be included in the corresponding DPS documents.

Table 5. Summary of Humoral Immunogenicity Assays

Assay	Purpose
Secondary endpoints	
SARS-CoV-2 neutralization (VNA)	Analysis of neutralizing antibodies to the wild-type virus and/or pseudovirion expressing S protein
SARS-CoV-2 binding antibodies (ELISA)	Analysis of antibodies binding to the SARS-CoV-2 S protein
Exploratory endpoints	
SARS-CoV-2 neutralization (neutralization assay)	Analysis of neutralizing antibodies to the vaccine strain (or other strain), as measured by an alternative neutralization assay (different from the VNA used for the secondary endpoint)
SARS-CoV-2 binding antibodies (ELISA)	Analysis of antibodies binding to the SARS-CoV-2 N protein, if such an assay can be developed
Adenovirus neutralization (neutralization assay)	Analysis of neutralizing antibodies to adenovirus
Functional and molecular antibody characterization	Analysis of antibody characteristics including Fc-mediated viral clearance, avidity, Fc characteristics, Ig subclass and IgG isotype
Epitope-specificity characterization	Analysis of site-specificity, epitope mapping
Cytokine profiling	Analysis of cytokines, chemokines, and other proteins of the innate or adaptive immune response in the serum or plasma
Passive transfer	Analysis of immune mediators correlating with protection against experimental SARS-CoV-2 challenge in a suitable animal model

ELISA = enzyme-linked immunosorbent assay; Ig = immunoglobulin; SARS-CoV-2 = severe acute respiratory syndrome coronavirus-2; VNA = virus neutralization assay

Table 6. Summary of Cellular Immunogenicity Assays

Assay	Purpose
Secondary endpoints	
Flow cytometry (ICS)	Analysis of T-cell responses to SARS-CoV-2 S protein, and/or other protein peptides by ICS including CD4 ⁺ /CD8 ⁺ , IFN γ , IL-2, TNF α , IL-4, IL-5, IL-13, and/or other Th1/Th2 markers
Exploratory endpoints	
ELISpot	IFN γ and IL-4 responses to SARS-CoV-2 S protein peptides by PBMCs, based on single ELISpot
Gene expression analysis	Analysis of gene expression by RNA transcript profiling and/or analysis of protein translates, in cells or whole blood stimulated with SARS-CoV-2 S protein peptides or in unstimulated cells or whole blood (ex vivo)
Cytokine profiling (ELISA or multiplexed arrays)	Analysis of cytokines, chemokines, and other proteins of the innate or adaptive immune response in cells or whole blood stimulated with SARS-CoV-2 S protein peptides, or in unstimulated cells or whole blood, by ELISA or multiplexed arrays and confirmation by functional in vitro assays
T and B cell phenotyping	Analysis of the phenotype of antigen-specific T and B cells, assessed by single cell analysis (on frozen or Smart tube isolated PBMCs)

ELISA = enzyme-linked immunosorbent assay; ELISpot = enzyme-linked immunospot (assay); ICS = intracellular cytokine staining; IFN γ = interferon gamma; IL = interleukin; PBMC = peripheral blood mononuclear cell; RNA = ribonucleic acid; S = spike; SARS-CoV-2 = severe acute respiratory syndrome coronavirus-2; TNF α = tumor necrosis factor alpha

7.7.1.2. Handling of Missing and/or Unquantifiable Immune Response Data

Missing immune response data will not be imputed.

Values below the lower limit of quantification (LLOQ) or limit of detection (LOD) will be handled as follows:

- Calculation of geomean and median:
 - o values <LLOQ are imputed with LLOQ/2.
- Calculation of fold increases from baseline:
 - o values <LLOQ are imputed with LLOQ.

Values above the upper limit of quantification (ULOQ) will be handled as follows:

- Calculation of geomean and median:
 - o Values >ULOQ are imputed with ULOQ.
- Calculation of fold increases from baseline:
 - o Values >ULOQ are imputed with ULOQ.

7.7.1.3. Handling of changes in assay status throughout the study conduct

In case of changes in assay status, from “qualified” to “validated”, the LLOQ and ULOQ are likely to change as well. If this should happen, then the SDTM database will contain records pertaining to the assay in the qualified status and records pertaining to the validated status, and the LLOQ and ULOQ values will also differ.

The statistical analysis will use the LLOQ and ULOQ values associated with the validated assay and will retrospectively apply these on all the data pertaining to the assay, including the data obtained while the assay status was “qualified”. This may imply that data received, statistically analyzed, and presented at an earlier time may change. Graphical displays will show the eventually used LLOQ and ULOQ values. Graphs and tables will have an additional footnote that reflects the assay status.

7.7.1.4. Immune Response Analysis

No formal hypothesis on immunogenicity will be tested.

7.7.1.5. Immunogenicity Against the Insert

7.7.1.5.1. Humoral Assays

For **VNA** (both wild-type virus and pseudovirion expressing S protein, as available), the following statistics will be calculated: N, geometric mean and corresponding 95% CI of the actual values, fold increase from baseline, fold increase from pre-dose 2 (if applicable, i.e. only for cohorts where a second dose is given in the primary regimen and for time points after dose 2), fold increase from pre-booster dose 1, fold increase from pre-booster dose 2, fold increase from pre-booster dose 3 (if applicable, i.e. only for cohorts 2a and 2b where booster doses are given and for time points after the said booster dose).

For the calculation of the geometric mean and its corresponding 95% CI, the arithmetic mean and its corresponding 95% CI are calculated on the \log_{10} transformed values. These values are back transformed to provide the geometric mean and its corresponding 95% CI.

For wild type and pseudovirion VNA separately:

- A sample will be considered positive if the value is strictly greater than the LLOQ ($>\text{LLOQ}$).
- Responder definition. A post-baseline sample will be considered a responder if at least one of the following conditions is satisfied:
 - The baseline sample value is less than or equal to the LLOQ ($\leq\text{LLOQ}$) and the post-baseline sample is strictly greater than the LLOQ ($>\text{LLOQ}$)
 - The baseline sample value is strictly greater than the LLOQ ($>\text{LLOQ}$) and the post-baseline sample value represents an at least 4-fold (≥ 4 -fold) increase from the baseline sample value.

Actual values are tabulated and shown as dot plots with dots for participant values, and the corresponding geometric mean and 95% CI per time point for each assay. In addition, GMT plots over time, combining the regimens in one graph (without individual participant dots) will also be generated.

Participant profiles of the actual values over time will be graphically presented.

Reverse distribution curves of the actual values are provided for selected time points.

In the graphs, original values will be displayed on the \log_{10} scale.

Further details and/or updated rules may be provided in the DPS.

For **S-ELISA**, the same as above applies.

The ratio of binding antibodies (S-ELISA) to wild type VNA, and the ratio of binding antibodies (S-ELISA) to pseudovirion expressing S protein VNA will be calculated for each time point. Values <LLOQ will be imputed with LLOQ for the calculation of the ratios. In addition, the ratio of the fold increase from baseline in binding antibodies (S-ELISA) to the fold increase from baseline in wild type VNA, and the ratio of the fold increase from baseline in binding antibodies (S-ELISA) to the fold increase from baseline in pseudovirion expressing S protein VNA will be calculated for each post-baseline time point. Values <LLOQ will be imputed with LLOQ for the calculation of the fold increase ratios. The following statistics will be calculated and tabulated: N, geometric mean and corresponding 95% CI of the ratio. Graphical displays will also be prepared, showing – for each time point – the geometric mean of the ratio and its 95% CI, together with the individual data points (dot plot).

If a similar assay is performed at different analyzing labs, then separate statistical analyses may be performed.

Scatterplots between humoral assay results will be provided for selected time points. These may include, but are not be limited to:

- Binding antibodies (S-ELISA) versus wild type VNA
- Binding antibodies (S-ELISA) versus pseudovirion expressing S protein VNA
- Wild type VNA versus pseudovirion expressing S protein VNA

If a similar assay is performed at different analyzing labs, then the statistical analyses may distinguish between these and provide separate scatterplots for each analyzing lab versus the other assay of interest. These scatterplots will display the values as analyzed for the geometric mean calculations, with values <LLOQ imputed with LLOQ (if an LLOQ is defined) and values >ULOQ imputed with ULOQ (if an ULOQ is defined). The LLOQ and ULOQ cut-off values per assay will be visualized in the scatterplots. Spearman correlation coefficients will also be provided (one per scatterplot).

7.7.1.5.2. Cellular Assays

For **ELISpot**, if available, at least the following statistics will be calculated: N, median, first and third quartile, minimum and maximum of the actual values. Additional statistics may be calculated and will be detailed in the DPS. The ELISpot in this study is planned to be two single ELISpot, measuring IFN-g and IL-4. In that case, the statistics will be analyzed for each cytokine separately.

For each cytokine, if available, the following is defined:

- Sample positivity:
 - For IFN-g: a sample will be considered positive if the value is strictly greater than the LOD (>LOD).
 - For IL-4: a sample will be considered positive if the value is strictly greater than the LOD (>LOD).

- Responder:

A post-baseline sample will be considered a responder if at least one of the following conditions is satisfied:

For IFN-g:

- The baseline sample value is less than or equal to the LOD (\leq LOD) and the post-baseline sample is strictly greater than the LOD ($>$ LOD)
- The baseline sample value is strictly greater than the LOD ($>$ LOD) and the post-baseline sample value represents an at least 3-fold (\geq 3-fold) increase from the baseline sample value.

For IL-4:

- The baseline sample value is less than or equal to the LOD (\leq LOD) and the post-baseline sample is strictly greater than the LOD ($>$ LOD)
- The baseline sample value is less than or equal to the LLOQ (\leq LLOQ) and the post-baseline sample is strictly greater than the LLOQ ($>$ LLOQ)
- The baseline sample value is strictly greater than the LLOQ ($>$ LLOQ) and the post-baseline sample value represents an at least 2-fold (\geq 2-fold) increase from the baseline sample value.

The SDTM database will contain the LOD and LLOQ values.

In keeping with the general derivation rules, values $<$ LLOQ are imputed with LLOQ/2 for the calculation of the median and with LLOQ for the calculation of the fold increases from baseline.

ELISpot values available in the database will already be background subtracted. No further background subtraction should be carried out. In case the SDTM data only contain peptide pools 1 and 2, but no combined peptide pool, then the combined peptide pool will be calculated as the sum of both peptide pools.

Tables with the descriptive statistics will be provided.

Participant profiles of the actual values over time will be graphically presented. For the graphs, original values will be displayed on the \log_{10} scale.

For ELISpot, the reported values are spot forming cells per million peripheral blood mononuclear cells (PBMC).

For ELISpot, IFN-g responses are considered Th1 and IL-4 responses are considered Th2. Due to this 1-to-1 correspondence, no separate Th1/Th2 analyses will be conducted for ELISpot.

Further details and/or updated rules may be provided in the DPS.

For **ICS**, if available, at least the following statistics will be calculated: N, median, first and third quartile, minimum and maximum of the actual values, number and percentage of participants with a positive sample (if available). Additional statistics may be calculated and will be detailed in the DPS.

It is planned to analyze the following cell populations at the time of the first interim analysis. The DPS may provide an updated version of this list, e.g. for subsequent analyses.

- CD4+:
 - IFN-g or IL2
 - IFN-g or IL2 NOT TH2
 - IL4 and CD40L
 - IL4 or IL5 or IL13 and CD40L
- CD8+:
 - IFN-g or IL2

The data received from the analyzing lab(s) will contain background subtracted values (“immediately reportable values”; i.e. background subtracted^a percentages of cells expressing the cytokine or cytokine combination). Negative background subtracted values will be imputed with zero prior to further processing.

The data will contain a positivity call for each cell population. Sample positivity should therefore not be further derived at the statistical analysis stage.

Tables will be provided that show the descriptive statistics mentioned above, structured as follows: CD4+/CD8+, peptide pool (as available in the database, e.g.: SARS-CoV2-S, SARS-CoV2-S1, SARS-CoV2-S2), cytokine (combination), and time point.

Participant profiles of the actual values over time will be graphically presented. For the graphs, original values will be displayed on the \log_{10} scale, with values <0.022% imputed with 0.011% (only for visual representation; calculations will be based on the actual values). The graphs that show individual participant’s data will visually differentiate between positive/negative samples (e.g. different symbols and/or different colors).

The reported values are percentage of cells expressing the cytokine(s).

Assessment of Th1/Th2 response ratio.

Based on the combined SARS-CoV2-S peptide pool, and using post baseline time points only, a Th1/Th2 response ratio will be calculated for samples that satisfy at least one of the following two conditions:

- a Th1 response (“IFN-g or IL2 NOT TH2”) that is both positive and $\geq 2 \times$ LLOQ,
- or
- a Th2 response (“IL4 or IL5 or IL13 and CD40L”) that is both positive and $\geq 2 \times$ LLOQ

^a Also known as “mock subtracted”

For the purposes of the Th1/Th2 ratio analysis, the LLOQ is 0.022% for both cell populations (Th1 and Th2).

If both cell populations (Th1 and Th2) are positive and $\geq 2 \times$ LLOQ, then the ratio of Th1/Th2 will be calculated as a numerical result.

If only one cell population (either Th1 or Th2) is positive and $\geq 2 \times$ LLOQ, then the following rules will be used to determine a qualitative assessment of the Th1/Th2 ratio:

- If one cell population is positive and the other is negative, then the positive cell population is greater than the negative cell population: if the Th1 response is positive and the Th2 response is negative, then the Th1/Th2 ratio will be set to “>1”. If the Th1 response is negative and the Th2 response is positive, then the Th1/Th2 ratio will be set to “<1”
- If both cell populations are positive, then the cell population that is $\geq 2 \times$ LLOQ is greater than the cell population that is $< 2 \times$ LLOQ: if the Th1 response is $\geq 2 \times$ LLOQ and the Th2 response is $< 2 \times$ LLOQ, then the Th1/Th2 ratio will be set to “>1”. If the Th1 response is $< 2 \times$ LLOQ and the Th2 response is $\geq 2 \times$ LLOQ, then the Th1/Th2 ratio will be set to “<1”.

For each post baseline time point, the number of participants with an evaluable Th1/Th2 response ratio will be tabulated, together with the number and percentage of participants with a Th1/Th2 ratio ≥ 1 and the number and percentage of participants with a Th1/Th2 ratio < 1 . Graphical display(s) of these data may also be produced.

Further details and/or updated rules may be provided in the DPS.

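### The IFN-g ELISpot responder rule starts its 3-fold test at the LOD but imputes at the LLOQ, so any baseline between the two limits needs more than the stated 3-fold rise

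*SAP*

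**What the plan says.** The ELISpot part of SAP section 7.7.1.5.2 gives each cytokine its own responder rule.

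- **IFN-g, first route:** baseline at or below the LOD, "and the post-baseline sample is strictly greater than the LOD".
- **IFN-g, second route:** "The baseline sample value is strictly greater than the LOD", "and the post-baseline sample value represents an at least 3-fold" increase from baseline.
- **IL-4:** the same LOD-crossing route, plus a route that IFN-g lacks: "The baseline sample value is less than or equal to the LLOQ", "and the post-baseline sample is strictly greater than the LLOQ". Its fold test (2-fold) applies only to baselines above the LLOQ.

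After these rules the section repeats the general convention of section 7.7.1.2: ELISpot values below the LLOQ "are imputed with LLOQ/2 for the calculation of the median and with LLOQ for the calculation of the fold increases from baseline". It adds that the database will hold the LOD and LLOQ values, but the SAP does not give them.

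In section 7.7.1.5.1 the VNA rule, which also serves for S-ELISA, uses the LLOQ both as the responder cut-off and as the imputation value.

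**The concern.** For IFN-g the cut-off that opens the fold test (LOD) and the value used to replace low results (LLOQ) are different limits. A participant whose baseline lies between them is excluded from the LOD-crossing route, has no LLOQ-crossing route, and enters the fold test with a baseline that has been raised. The criterion printed in the SAP is a 3-fold rise from the participant's own baseline; the criterion applied is a post-baseline value of at least three times the LLOQ.

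At stake is the classification of participants with a low but detectable pre-vaccination IFN-g response. The rule can call the larger of two rises a non-response. It also leaves room for two programmers to report different responder rates, depending on whether they apply the imputation inside the responder test.

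**Working it through.** The SAP states no figure on this point, so there is none to reproduce. The check applies the rules literally.

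**Inputs from section 7.7.1.5.2.** IFN-g: LOD-crossing route; fold route for baseline >LOD with threshold 3. IL-4: LOD-crossing and LLOQ-crossing routes; fold route for baseline >LLOQ with threshold 2. Values <LLOQ set to LLOQ for fold increases. **Assumed:** R = LLOQ/LOD, because neither limit is given.

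**Step 1: rise needed when LOD < b < LLOQ.**

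- IFN-g as written: post/LLOQ ≥ 3, so post ≥ 3×LLOQ and the measured rise is at least 3×LLOQ/b. This runs from just above 3 (b near LLOQ) to just under 3R (b near LOD); at the geometric middle of the band it is 3√R.
- IFN-g on unimputed values: exactly 3.
- IL-4: post > LLOQ, a rise above LLOQ/b, between 1 and R.

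| R | IFN-g as written | mid-band | IL-4 |
|---|---|---|---|
| 1 | no band | – | – |
| 1.25 | 3 to 3.75 | 3.35 | 1 to 1.25 |
| 1.5 | 3 to 4.5 | 3.67 | 1 to 1.5 |
| 2 | 3 to 6 | 4.24 | 1 to 2 |
| 3 | 3 to 9 | 5.20 | 1 to 3 |
| 5 | 3 to 15 | 6.71 | 1 to 5 |

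**Step 2: coherence at the LOD.** Take LOD = 1 and LLOQ = 2 for illustration.

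- 0.9 to 1.1 (1.2-fold): IFN-g responder, by crossing the LOD.
- 1.1 to 5.9 (5.4-fold): not an IFN-g responder, since 5.9/2 = 2.95. It is a responder on unimputed values.
- 1.9 to 5.9 (3.1-fold): not an IFN-g responder, for the same reason.
- 2.1 to 6.3 (3.0-fold): IFN-g responder.

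The post-baseline value required jumps from just above 1 to 6 as the baseline passes the LOD. On unimputed values it would jump only to 3.

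**Step 3: the sister rules.** In the IL-4 and VNA/S-ELISA rules a baseline at or below the LLOQ qualifies by crossing the LLOQ, and the fold test is kept for baselines above it. No imputed baseline enters either fold test.

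**Step 4: illustrative size within the band.** Assume baselines log-uniform between LOD and LLOQ and a rise with median 4-fold and log10 SD 0.25. The share with a rise of at least 3-fold is Φ(log10(4/3)/0.25) = Φ(0.50) = 69%. As written, the share is the average of Φ((log10(4/3) − u)/0.25) for u from 0 to log10 R:

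| R | as written | unimputed | IL-4 structure |
|---|---|---|---|
| 1.25 | 62% | 69% | – |
| 1.5 | 56% | 69% | – |
| 2 | 46% | 69% | 96% |
| 3 | 35% | 69% | 90% |

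**Step 5: illustrative size over all participants.** Assume log-normal baselines (median 1.5×LOD, SD 0.9 on the natural-log scale) and rises (median 4-fold, SD 0.8), with R = 2. About 30% of baselines fall in the band. IFN-g responders in the band: 47% as written, 64% unimputed, 90% with the IL-4 structure. Over all participants: 64%, 69% and 77%. The first gap agrees with 30% × (64% − 47%) ≈ 5 points. At R = 1.5 the overall figures are 67.9% as written and 69.6% unimputed.

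**The case against.** **Little rests on this rule.** ELISpot is exploratory (section 7.5 and Table 6) and reported only if available. The minimum ELISpot statistics listed are N, median, quartiles and range, with no responder percentage, and section 7.7.1.4 says no immunogenicity hypothesis is tested. This stands and limits the weight of the point. But the SAP does define an IFN-g responder, and any rate reported will use that definition.

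**The effect may not exist.** If LOD and LLOQ coincide for IFN-g, there is no band. The rule is written on the LOD alone, so the author may have had that in mind. This stands as a condition; nothing in the SAP says that the limits coincide.

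**The fold could be read as unimputed.** Then the test is exactly 3-fold. That reading is possible, but the imputation sentence sits in the same section and covers fold increases from baseline without exception. At best the definition is open.

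**Values below the LLOQ are not quantifiable, and raising them to the LLOQ is conservative.** This is a fair argument against relying on a raw fold. It does not explain why IFN-g has no LLOQ-crossing route when IL-4, under the same convention, does.

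**The Data Presentation Specifications may update the rules.** That is a place to make the correction, not a reason to leave it unmade.

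A reader might also infer that Th1 responses are under-called relative to Th2, because "IFN-g responses are considered Th1 and IL-4 responses are considered Th2". With common limits, IFN-g needs three times the IL-4 rise within the band, against 1.5 times (3-fold versus 2-fold) above the LLOQ. But the two assays may have different limits, and the 3- versus 2-fold difference is an openly stated choice. Within the band the two rules disagree only when the post-baseline value lies above the LLOQ and below 3×LLOQ. The SAP plans no separate ELISpot Th1/Th2 analysis; its planned Th1/Th2 ratio comes from ICS, which this rule does not touch. A biased Th1/Th2 comparison is therefore not something the document supports.

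**Conclusion.** The point holds in limited form. If the LLOQ exceeds the LOD for the IFN-g ELISpot, and the imputation is applied in the responder test as the section indicates, the stated 3-fold criterion is not the one applied to baselines between the limits. The rule is also incoherent at the LOD.

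The excess over 3-fold is a factor LLOQ/b, between 1 and LLOQ/LOD. It would be wrong to say that all these participants need far more than a 3-fold rise: near the LLOQ, or with limits close together, the excess is small. In the illustrations with R = 2, the shortfall against an unimputed 3-fold test is 17 to 23 percentage points within the band and about 5 points overall. These figures rest on assumed limits, baselines and rises. The true effect on IFN-g responder rates, and on any informal reading of IFN-g against IL-4, is unknown.

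**What to change.** Make the cut-off and the imputation value agree for IFN-g, in the SAP or in the Data Presentation Specifications, before responder rates are produced. Two ways are open:

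1. **Compute the responder fold from unimputed values whenever the baseline is above the LOD.** This keeps the stated 3-fold criterion. The cost is reliance on baselines below the LLOQ, which are measured imprecisely.
2. **Adopt the IL-4 structure:** keep the LOD-crossing route, add baseline ≤LLOQ with post >LLOQ, and apply the 3-fold test only to baselines >LLOQ. No imputed baseline then enters the test. The cost is that a small rise across the LLOQ counts as a response, and the responder rate in the band goes up clearly (46% to 96% in the first illustration at R = 2). A step in the required value remains at the LLOQ, from LLOQ to 3×LLOQ.

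Neither option changes the LOD-crossing route, so a small rise across the LOD still counts under both. Either is a short change of wording and programming. The IFN-g LOD and LLOQ should be stated alongside, so that a reader can see whether the band exists.
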